1.0 BACKGROUND INFORMATION

The Alzheimer's Association (2004) estimates that clinically significant depression occurs in about 20 to 40 percent of people with Alzheimer disease. The percentage increases to 70 to 80 percent for Alzheimer residents in assisted care facilities. Treatment of depression in Alzheimer disease can improve sense of well-being, quality of life, and individual function, even in the presence of ongoing decline in memory and thinking. In institutionalized settings, lack of sufficient exposure to bright light is considered one of the primary contributors to disruption of the circadian system, with cascading effects of sleep disruption, agitated behavior, depression, and cognitive decline (Day et al., 2000). Exposure to bright light (2500 - 10,000 lux) typically administered in the morning, has been shown through a large body of research to be an effective non-pharmaceutical treatment option for depression (Golden, et al., 2005). Light therapy has also been shown to be an effective treatment for sleep disturbances (Dowling, et al., 2005) and for ameliorating behavioral problems (Cohen-Mansfield, 2001) for people with Alzheimer disease. However, reliable and well-designed studies examining the efficacy of light therapy in treating depression among people with Alzheimer disease are extremely limited (Forbes et al., 2009). Moreover, the conventional approach to administering the bright light stimulus, through boxes containing arrays of fluorescent light fixtures, is problematic for people with Alzheimer disease due to reported side effects of headache, eye strain, nausea, and agitation (Labbate 1994; Terman, 1999). We hypothesize that exposure to sufficient daylight indoors can serve as an effective non-drug treatment option for people with Alzheimer disease and depression, with the potential to lead to fewer adverse effects than noted with light box treatments. Aside from the intervention, the residents and staff participating in this study will not experience any changes to their normal routine and duties. Staff supervised socialization can, but does not necessarily include interaction with other residents in the facility or engagement in "free time" activities such as watching TV. We are aware that any changes outside of the intervention, either with staff specified roles or residents could potentially interfere with the results of the study.

2.0 OBJECTIVES AND PURPOSE

This study is designed to test the hypothesis that an intervention increasing exposure to daylight will reduce depression and negative behaviors and increase cognitive function among Alzheimer patients in Los Angeles dementia care facilities.

3.0 STUDY DESIGN

The research will be conducted as a 12-week field study in eight Silverado dementia care facilities in Los Angeles and Orange County. Silverado is an assisted living service provider that delivers care for those with Alzheimer, dementia and other memory-impairing diseases. Data collection will occur twice during the study: baseline measures at the beginning of the study and outcome measures at the end of the study.

4.0 TREATMENT OF SUBJECTS

4.1 Intervention Group

At two facilities, the active light intervention will enlist staff to increase daylight exposure to Alzheimer residents by taking them to daylit perimeter room in the morning (8:00 - 10:00 AM) where vertical daylight illuminance at eye level exceeds 2500 lux and where direct sun exposure

can be avoided. The intervention will consist of two hours of daylight exposure administered beginning at 8:00 AM in the morning each day (7 days / week) over the 12-week study.

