4.2 Control Group

Patients at the other two facilities will receive usual care. During the period from 8:00 AM to 10:00 AM each day, the control group of Alzheimer residents will be taken to a similar sized area indoors without daylight exposure for socialization under typical interior fluorescent lighting conditions.

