5.0 SELECTION AND EXCLUSION OF SUBJECTS

5.1 Inclusion criteria for enrollment

The trial inclusion criteria is an AD diagnosis and no physical co-morbidities that preclude participation in the daily group intervention. Based on current facility records, we estimate the intervention and control groups will include approximately 160 Alzheimer disease participants total (20 patients per facility). Demographic information obtained during the study preparation phase (mean age, gender, type of dementia by diagnosis, depression level, length of time in facility, date of onset of dementia, ethnicity) will be obtained to show that the facilities are comparable.

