6.0 STATISTICS

All analyses will include factors for facility and intervention (nested within facility). Baseline analyses will include descriptors of the study sample (age, gender, ethnicity, onset of Alzheimer's disease) as well as initial levels of the outcome measures (depression, cognition, behavior) and will utilize analysis of variance for continuous data and chi-square methods for categorical data to compare the intervention groups. If the intervention groups are found to differ on baseline levels of the outcome variables or other variables related to outcome, these variables will be included as adjusting covariates in the comparisons of 12-week outcomes. 12-week outcomes will be compared between intervention groups with analysis of variance (2-level factor for intervention, 8-level factor for facility, with intervention nested within facility). For planning of larger trials, the following estimates will be made (along with 95% confidence intervals) for each patient outcome: intervention effect size (mean group difference in outcome), variance in outcome (across patients, across facilities), within-facility correlation in outcomes (correlations in outcomes amongst patients within a facility), within-patient correlation in outcomes (repeated measures, baseline and 12-weeks).

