6.1 Sample Size

As a pilot study, the planned sample size is not based on statistical power to detect specified effect sizes on intervention outcomes. Rather, the planned sample of 80 subjects per intervention group was selected in terms of pilot study feasibility. The planned sample is considered more than sufficiently adequate to address pilot trial questions related to feasibility (of study recruitment and conduct, delivery of intervention, data collection) and estimates of trial-related parameters, along with 95% confidence intervals (mean intervention effect size, variance in outcome measures in the study population, within-facility correlation in outcome measures, within-patient correlation in outcome measures). As pilot studies are well known to over-estimate intervention effect sizes and under-estimate measures of variance, it is crucial that confidence intervals (precision of the estimates) are also calculated and available for planning of larger studies.

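### Sections 4.1 and 4.2 allocate four facilities, two per arm, but the rest of the plan is built on eight facilities, about 160 patients and 80 per arm

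*Combined protocol and SAP*

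**What the plan says.** The only text that places facilities in arms is in Sections 4.1 and 4.2. Section 4.1 reads "At two facilities, the active light intervention will enlist staff to increase daylight exposure to Alzheimer residents". Section 4.2 reads "Patients at the other two facilities will receive usual care". The wording of 4.2 closes the set: two plus two, with none left over.

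Four other sections describe a larger study, each supplying a different piece:

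- Section 3.0: "12-week field study in eight Silverado dementia care facilities".
- Section 5.1: "approximately 160 Alzheimer disease participants total (20 patients per facility", a figure based on facility records.
- Section 6.0, the model for the 12-week outcomes: "2-level factor for intervention, 8-level factor for facility, with intervention nested within facility".
- Section 6.1: "the planned sample of 80 subjects per intervention group was selected in terms of pilot study feasibility". The same section says that "the planned sample size is not based on statistical power to detect specified effect sizes on intervention outcomes".

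No section mentions a second wave, a crossover, a third arm or reserve sites. Section 3.0 describes one 12-week period with measurement at its start and end.

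**The concern.** Treatment is given to whole facilities, so the number of facilities per arm is the allocation. Someone following Section 4 would run the study in four facilities and would not know what the other four in Section 3.0 should do. The sample in Section 6.1 could not then be reached at the facility size in Section 5.1, and the eight-level factor in Section 6.0 could not be fitted to data from four facilities.

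The facility count also governs what the pilot can deliver. Sections 4.3, 6.0 and 6.1 list the intervention effect, the outcome variances and the within-facility correlation, with confidence intervals, as products for planning larger trials. Section 6.0 includes the variance across facilities among them. Information on between-facility variation comes from the number of facilities, and two per arm give very little.

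**Working it through.** **Inputs from the documents.** Eight facilities (3.0); two intervention facilities (4.1); two control facilities (4.2); 20 patients per facility and about 160 in total (5.1); eight facility levels (6.0); 80 patients per group (6.1).

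**Step 1. Reproduce the stated sample.** Total = facilities × patients per facility = 8 × 20 = 160, as in 5.1. Per arm with an equal split = 160 / 2 = 80, as in 6.1. Facilities per arm implied = 80 / 20 = 4. Sections 3.0, 5.1, 6.0 and 6.1 therefore fit together, but only with four facilities in each arm.

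**Step 2. Apply the Section 4 allocation.**

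| Quantity | From 4.1 and 4.2 | Stated elsewhere |
|---|---|---|
| Facilities | 2 + 2 = 4 | 8 (3.0) |
| Patients per arm | 2 × 20 = 40 | 80 (6.1) |
| Patients in total | 4 × 20 = 80 | about 160 (5.1) |
| Levels of the facility factor | 4 | 8 (6.0) |
| Facilities without an arm | 8 − 4 = 4 | not addressed |

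**Step 3. Could larger facilities close the gap?** Two facilities per arm would need 80 / 2 = 40 patients each, twice the stated 20. The total in 5.1 is approximate, but that does not cover a factor of two.

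**Step 4. Illustration of what the count does to precision.** This step is not needed for the conclusion. It assumes an error term at facility level, exactly 20 patients per facility, no attrition, no covariate adjustment and an intraclass correlation (ICC) from 0 to 0.20. The documents give no ICC. With k facilities per arm, and in units of the outcome SD,

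half-width of the 95% CI = t(0.975; 2k − 2) × √{2 × [ICC + (1 − ICC)/20] / k}.

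| ICC | k = 4 (6 df, t = 2.447) | k = 2 (2 df, t = 4.303) |
|---|---|---|
| 0 | 2.447 × 0.1581 = 0.387 | 4.303 × 0.2236 = 0.962 |
| 0.05 | 0.540 | 1.344 |
| 0.10 | 0.659 | 1.638 |
| 0.20 | 2.447 × 0.3464 = 0.848 | 4.303 × 0.4899 = 2.108 |

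The ratio is (4.303 / 2.447) × √2 = 2.49 at every ICC.

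**The case against.** The strongest reply is that the intention is plain. Four sections agree on eight facilities, the stated sample reproduces exactly from them, and only the two counts in Section 4 stand out. No product or sum in the plan is itself wrong, and Section 5.1 takes its figure from facility records, not from Section 4. The study is also a pilot without a power calculation, so no power claim fails. All of this is correct, and eight is probably what is meant. It does not remove the need for correction: the two sentences at odds with the rest are the only ones that define the arms, and a split of four and four is written nowhere.

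A second reply concerns the illustration. Section 6.0 does not say that facility is a random effect. With facility fixed and a patient-level residual, the degrees of freedom would be 160 − 8 = 152 against 80 − 4 = 76, and the interval would widen by only about √2, roughly 1.4. That is fair. The factor of 2.49 belongs to the facility-level error term assumed above, and the finding does not rest on it.

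Third, Section 6.0 describes intervention as nested within facility, which taken literally could suggest both conditions inside each facility. Sections 4.1 and 4.2 plainly assign whole facilities, and the literal reading would not explain a count of two and two in any case.

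**Conclusion.** The concern holds. The allocation in Sections 4.1 and 4.2 covers four facilities and yields 40 patients per arm and 80 in total. The plan states eight facilities, 80 per arm and about 160 in total, a factor of two throughout. Four facilities have no stated arm. This rests only on counts in the documents and the stated 20 patients per facility.

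If the Section 4 counts were the true ones, the interval for the effect would be about 2.5 times as wide under a facility-level error term: 0.96 to 2.11 SD instead of 0.39 to 0.85 SD for an assumed ICC of 0 to 0.20.

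The documents do not say which count is current. The correction is required because, as written, neither the sample size nor the analysis model can be obtained from the stated allocation.

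**What to change.** Reconcile Sections 4.1 and 4.2 with Sections 3.0, 5.1, 6.0 and 6.1, so that every participating facility has a stated arm.

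- **If eight facilities and 80 per group are intended:** state four facilities per arm in 4.1 and 4.2. This number is inferred from 80 / 20 and should be confirmed by the sponsor.
- **If only four facilities take part:** change eight to four in 3.0, 160 to 80 in 5.1, the eight-level factor to four levels in 6.0, and 80 per group to 40 in 6.1.

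In either case, give the number of facilities per arm in Section 6.1 beside the number of patients per arm, since the precision of the planning estimates depends on both.

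The first option costs only a change of wording. The second halves the stated sample on paper. Neither calls for extra patients or data collection.

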4.2 Control Group

Patients at the other two facilities will receive usual care. During the period from 8:00 AM to 10:00 AM each day, the control group of Alzheimer residents will be taken to a similar sized area indoors without daylight exposure for socialization under typical interior fluorescent lighting conditions.

4.3 Outcome Measures

The following outcome measures will be taken:

- 1. Patient outcomes will be completed at baseline and 12-weeks. For each of our major outcomes, we will use instruments that are well-validated for use in testing effects of short- to long-term interventions in AD:
 - a. Depression: Cornell Scale for Depression in Dementia (CSDD)
 - b. Neuropsychiatric Inventory Nursing Home Version (NPI-NH)
- 2. Trial conduct/methods outcomes:
 - a. Facility and staff support and participation: facilitators and obstacles.
 - b. Fidelity of light and control intervention: facilitators and obstacles.
 - c. Data collection fidelity: patient outcomes and light measures.
 - d. Estimates of subject recruitment, consent, and attrition rates: facilitators and obstacles.
 - e. Estimates (and confidence intervals) for study/trial planning: intervention effect size, variance of outcome measures, within-facility correlation in outcome measures, within-patient correlation in outcome measures (repeated measures).

4.4 Lighting Measures

Physical lighting measurements will be recorded continuously at 1-minute intervals throughout the study using research grade photometric sensors and data logging equipment to establish 24-hour patterns of light / dark exposure. Additionally, in-situ measurements will be taken using a spectrometer to assess the spectral power distribution of light exposure at seated eye level.

5.0 SELECTION AND EXCLUSION OF SUBJECTS

5.1 Inclusion criteria for enrollment

The trial inclusion criteria is an AD diagnosis and no physical co-morbidities that preclude participation in the daily group intervention. Based on current facility records, we estimate the intervention and control groups will include approximately 160 Alzheimer disease participants total (20 patients per facility). Demographic information obtained during the study preparation phase (mean age, gender, type of dementia by diagnosis, depression level, length of time in facility, date of onset of dementia, ethnicity) will be obtained to show that the facilities are comparable.

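### The plan does not say how facilities are assigned to daylight or control, and resident descriptors from so few facilities cannot show that the two sets are comparable

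*Combined protocol and SAP*

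**What the plan says.** Section 3.0 describes a 12-week field study at eight facilities of one operator. Section 4.1 begins: "At two facilities, the active light intervention will enlist staff to increase daylight exposure". Section 4.2 continues: "Patients at the other two facilities will receive usual care". Neither section, nor 3.0, says how a facility gets its condition. An opening part of the document was not available for review, so this holds for the supplied text only.

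Two provisions bear on comparability.

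- Section 5.1 lists resident descriptors (age, gender, dementia type, depression level, time in the facility, onset, ethnicity) that "will be obtained to show that the facilities are comparable".
- Section 6.0 compares the intervention groups at baseline by analysis of variance or chi-square, and makes adjustment conditional: "If the intervention groups are found to differ on baseline levels of the outcome variables or other variables related to outcome", those variables become covariates.

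On purpose, Section 2.0 states: "This study is designed to test the hypothesis that an intervention increasing exposure to daylight will reduce depression". Sections 6.0 and 6.1 pass the effect estimate and its 95% confidence interval on to later trials. Section 6.1 adds that "it is crucial that confidence intervals (precision of the estimates) are also calculated and available for planning of larger studies".

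**The concern.** The facility is the unit that receives the condition, so the way facilities are assigned decides what the difference between arms can mean. Daylight sites need a room that meets the illuminance requirement of Section 4.1. Control residents "will be taken to a similar sized area indoors without daylight exposure". Nothing requires each facility to have both kinds of space, so the plan leaves open that the building, or something that goes with it, decides the arm.

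The descriptors cannot fill that gap, for two reasons. With four or eight facilities, a comparison of arms is too imprecise for an absence of difference to be informative. And the listed variables describe residents: no building, staffing or care-practice variable is named for comparison or adjustment.

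At stake is the effect estimate. A systematic difference between the chosen sites would enter it as bias, and a confidence interval built from variation between facilities makes no allowance for that. Recruitment, attrition, fidelity, variance and correlation estimates depend much less on how sites were assigned.

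**Working it through.** **Number of facilities.** Section 5.1 gives 20 residents per facility and about 160 in total: 8 × 20 = 160. Section 6.1 gives 80 per group: 160 / 2 = 80, and 80 / 20 = 4 facilities per arm. This agrees with the eight facilities of 3.0 and the 8-level factor of 6.0. The two-plus-two of 4.1 and 4.2 gives 4 × 20 = 80 in total, which does not reproduce 160. Both counts are worked below.

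**What a baseline comparison can show.** From the plan: 20 residents per facility, and k = 4 or 2 facilities per arm. Assumed, because the documents give no value: ICC 0.01 to 0.20, a true gap of 0.5 SD, and a two-sided 5% test on facility means.

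- Variance of a facility mean, in SD units: ICC + (1 − ICC)/20
- SE of the difference between arms: √(2 × variance / k)
- Power: noncentral t with 2k − 2 df and noncentrality 0.5/SE

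Example, ICC 0.05 and k = 4: variance = 0.05 + 0.95/20 = 0.0975; SE = √(0.0975 × 2/4) = 0.221; noncentrality = 0.5/0.221 = 2.26 on 6 df; power 48%.

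| ICC | SE, 4 v 4 | Power, 4 v 4 | 95% CI half-width, 4 v 4 (SD) | Power, 2 v 2 | 95% CI half-width, 2 v 2 (SD) |
|---|---|---|---|---|---|
| 0.01 | 0.172 | 68% | 0.42 | 23% | 1.05 |
| 0.05 | 0.221 | 48% | 0.54 | 16% | 1.34 |
| 0.10 | 0.269 | 35% | 0.66 | 13% | 1.64 |
| 0.20 | 0.346 | 23% | 0.85 | 10% | 2.11 |

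**What selection of sites could do.** Suppose the top four of eight sites on some trait all receive one condition. The expected difference between the top-four and bottom-four means of eight standard normals is 1.450. With r the facility-level correlation between trait and outcome, the bias before baseline adjustment is r × 1.450 × √ICC. For r = 0.5 and ICC 0.10: 0.5 × 1.450 × 0.316 = 0.23 SD. Coverage of a facility-level 95% CI (6 df) comes from 200,000 simulated studies. Under random assignment it is 95%.

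| r | Bias, ICC 0.05 (SD) | Coverage | Bias, ICC 0.10 (SD) | Coverage |
|---|---|---|---|---|
| 0.1 | 0.03 | 95% | 0.05 | 95% |
| 0.3 | 0.10 | 93% | 0.14 | 93% |
| 0.5 | 0.16 | 90% | 0.23 | 88% |

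**What randomising does and does not do.** Under random 4:4 assignment, chance facility imbalance has SD √(ICC × 2/4): 0.16 at ICC 0.05 and 0.22 at ICC 0.10. Randomising leaves this error in place, but a facility-level interval then covers it.

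**The case against.** **The two provisions may be modest.** Section 5.1 names no test and may describe a check of sites during preparation. Section 6.0 uses its comparison to choose covariates and does not say that a null result proves comparability. That is a fair reading of 6.0. But 5.1 does state showing comparability as its aim, and the half-widths above apply to any comparison of arms, tested or only described.

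**The power figures depend on assumptions and on the error term, which 6.0 does not name.** This stands. A patient-level test that ignores clustering would have 86% to 72% power with 4 per arm over the same ICC range, and would flag 7% to 38% of comparisons with no systematic gap. Those false flags are a separate error-term problem and are not counted here. Even that test would miss a 0.5 SD gap in 14% to 28% of cases.

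**The modelled harm is limited.** This also stands. The scenario is extreme, the bias is at most about 0.4 of the interval's half-width, and coverage stays at about 93% or more for correlations up to 0.3. No bias was computed after baseline adjustment, so the figures do not describe the planned analysis where adjustment is triggered.

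**This is a pilot, with one operator and unchanged routines.** Section 6.1 explains the absence of a power calculation. It does not explain a missing assignment method when an effect estimate is a planned output. The shared operator and the similar control area limit differences between facilities without settling which facility gets which condition.

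**A stronger reading.** A reader might infer that sites were hand-picked, for instance for their daylight, and that the estimate is therefore biased. The documents do not say so; they are silent on assignment.

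**Conclusion.** The point holds as a gap in the design that should be closed, without invalidating the pilot. The supplied text gives no assignment method, and what it offers towards comparability cannot show it: 68% to 23% power for a 0.5 SD gap with 4 facilities per arm, 23% to 10% with 2. As written, the plan does not support a causal reading of the effect estimate under Section 2.0, and later planners could not tell what that estimate and its interval represent.

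The possible cost, if sites were selected on an outcome-related trait, is about 0.03 to 0.23 SD of unadjusted bias, with coverage of 95% down to 88%. This rests on assumed ICCs of 0.05 and 0.10, assumed correlations of 0.1 to 0.5, eight facilities and a facility-level interval. It would go too far to say that the pilot's other outputs are compromised, or that randomising would make so few facilities balanced.

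**What to change.** 1. Reconcile the number of facilities first: eight (3.0, 5.1, 6.0) against two plus two (4.1, 4.2). With eight, 4:4 assignment gives 70 possible allocations; with four, 2:2 gives only 6.
2. Add to 3.0, for example: *Before the start, each facility is confirmed to have both a qualifying daylit room and a similar area without daylight. Facilities are then randomised in equal numbers to the two conditions. Where feasible, a facility's condition is revealed only after representative consent and baseline CSDD and NPI-NH are complete there.*
3. In 5.1, change the stated aim of the descriptors to: *to describe the facilities by condition*.
4. If sites are already fixed, or lack both room types, do not replace them. State how they were chosen and report the effect estimate as a non-randomised cluster comparison.

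Cost: steps 2 and 3 need one room check, one allocation step, a sequencing rule and a change of wording, at sites of a single operator. The team loses free choice of intervention sites, and chance imbalance remains. Step 4 costs only wording.
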